1. AMENDMENTS FROM PREVIOUS VERSION(S)

Version	Date	Summary of amendments	Author
1.0	2021-11-30	None (First version)	PPD
2.0	2022-04-08	Added safety analysis of Blood Sugar Test (BST)	PPD

2. INTRODUCTION

This SAP described a statistical analysis plan for the **CCI** study. It was written based on the BE Study Protocol, and the analysis plan follows **PPD** SOP and the finally approved BE Study Protocol. If there is a difference between SAP and SOP, the one specified in SAP shall be given a priority.

2.1 STUDY OBJECTIVES

2.1.1 Primary Objectives

To demonstrate the bioequivalence of the newly developed "Glucophage® XR Reduced Mass tablet" (containing metformin hydrochloride 500 mg) and the current marketed "Glucophage® XR tablet" (containing metformin hydrochloride 500 mg) after single oral administration under fasted and fed conditions.

2.1.2 Secondary Objectives

- To evaluate the safety and tolerability of the metformin formulations after single dose treatment under fasted and fed conditions.
- To characterize other PK parameters of the metformin formulations under fasted and fed conditions.

2.2 STUDY DESIGN

This bioequivalence study is divided into two parts according to the method of administration of the Investigational Medicinal Products (IMPs): Part 1 (Fasted state) and Part 2 (Fed state).

Each part of the study is performed by an open label, randomized, 2-period, 2-sequence, single oral dose and crossover design.

A detailed description of the study design is specified in Table of Contents 4 of the BE Study Protocol.

2.3 SAMPLE SIZE

Eighty-two (82) healthy adult subjects will be included in the study: 48 in the fasted group (Part 1) and 34 in the fed group (Part 2).

1) Part 1: Fasted state (N=48)

Variability estimates were obtained from the preliminary PK data **CCI** [fasted] and **CCI** [fed]) and intra-subject variability of the major pharmacokinetic parameters AUC_{last} and C_{max} of metformin were about 19.1 % and 25.0%, respectively. Based on the intra-subject variability of the C_{max} , the difference of log-transformed mean values of the evaluation parameters of Reference Drug and Test Drug was used as log 0.95. Sample size of 19 subjects per sequence, totally 38 subjects meeting 2-period 2-sequence crossover study design, has significance level of 0.05 and a power of 90%. Considering the dropout rate (about 20%) during the study, 24 subjects per sequence, totally 48 subjects will be recruited.

2) Part 2: Fed state (N=34)

Variability estimates were obtained from the preliminary PK data **CCI** [fasted] and **CCI** [fed]) and intra-subject variability of the major pharmacokinetic constants AUC_{last} and C_{max} of metformin were about 13.1% and 18.7%, respectively. Based on the intra-subject variability of the C_{max} , the difference log of log-transformed mean values of the evaluation parameters of Reference Drug and Test Drug was used as log 0.95. Sample size of 11 subjects per sequence, totally 22 subjects meeting 2-period 2-sequence crossover study design, has significance level of 0.05 and a power of 90%. Considering the dropout rate (about 35%) during the study, 17 subjects per sequence, totally 34 subjects will be recruited.

- R: Glucophage® XR tablet (Reference Drug)
- T: Glucophage® XR Reduced Mass tablet

Part	Sequence	Period		
		1	Washout	2
Part 1 (n=48)	1(n=24): RT	R	≥ 7 days	T
	2(n=24): TR	T		R

Part	Sequence	Period		
		1	Washout	2
Part 2 (n=34)	1(n=17): RT	R	≥ 7 days	T
	2(n=17): TR	T		R

3. HYPOTHESES AND DECISION RULES

3.1 STATISTICAL HYPOTHESES

The alternative hypothesis ($H_1: \theta_L \leq \mu_T - \mu_R \leq \theta_U$) and null hypothesis ($H_0: \mu_T - \mu_R < \theta_L$ or $\mu_T - \mu_R > \theta_U$) of BE Study can be expressed as two one-sided hypotheses:

- $H_{0A}: \mu_T - \mu_R < \theta_L, \quad H_{1A}: \theta_L \leq \mu_T - \mu_R$
- $H_{0B}: \mu_T - \mu_R > \theta_U, \quad H_{1B}: \mu_T - \mu_R \leq \theta_U$

μ_T and μ_R are the geometric mean of C_{max} and AUC, respectively, and $[\theta_L, \theta_U] = [0.80, 1.25]$ defines the acceptance range of bioequivalence. Bioequivalence will be tested for both Part 1 and Part 2. Overall, bioequivalence can be concluded if all 8 null hypotheses (H_{0A} and H_{0B} for both AUC and C_{max} , in Part 1 and in Part 2) can be rejected with an alpha of 5%.

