9.2.2 Sample Size Justification

1) Part 1: Fasted state (N=48)

Variability estimates were obtained from the preliminary PK data (CCI [fasted] and CCI [fed]) and intra-participant variability of the major pharmacokinetic parameters AUC_{last} and C_{max} of metformin were about 19.1 % and 25.0%, respectively. Assuming a within-participant variability $CV\% = 25\%$, and with an assumed geometric mean ratio Test/Reference (GMR T/R) of 0.95, a one-sided alpha level of 0.05, 38 evaluable participants will be needed to provide approximately 90% power to show bioequivalence. Considering the drop-out rate (about 20%) during the study, 24 participants per sequence, totally 48 participants will be recruited.

2) Part 2: Fed state (N=34)

Variability estimates were obtained from the preliminary PK data (CCI [fasted] and CCI [fed]) and intra-participant variability of the major pharmacokinetic constants AUC_{last} and C_{max} of metformin were about 13.1% and 18.7%, respectively. Assuming a within-participant variability $CV\% = 18.7\%$, and with an assumed geometric mean ratio Test/Reference (GMR T/R) of 0.95, a one-sided alpha level of 0.05, 22 evaluable participants will be needed to provide approximately 90% power to show bioequivalence. Considering the drop-out rate (about 35%) during the study, 17 participants per sequence, totally 34 participants will be recruited.

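### Is the stated 90% power misleading when the SAP's overall conclusion needs both parts of the study to succeed?

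*SAP*

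**What the plan says.** Protocol 9.2.2 treats each part under its own heading. For Part 1 (fasted) the within-participant CVs for AUClast and Cmax "of metformin were about 19.1 % and 25.0%, respectively", and "38 evaluable participants will be needed to provide approximately 90% power to show bioequivalence". For Part 2 (fed) they "of metformin were about 13.1% and 18.7%, respectively", and "22 evaluable participants will be needed to provide approximately 90% power to show bioequivalence". Both calculations are made "with an assumed geometric mean ratio Test/Reference (GMR T/R) of 0.95" and use "a one-sided alpha level of 0.05". SAP 2.3 repeats the two calculations, again part by part, and the protocol synopsis does the same.

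SAP 3.1 defines the study-level conclusion: "Overall, bioequivalence can be concluded if all 8 null hypotheses" are rejected, that is, the lower and upper one-sided nulls for AUC and Cmax in Part 1 and in Part 2. Neither document gives a power for that conclusion.

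The protocol frames its own test by part. Section 9.1 requires both parameters to pass, with test and reference compared under fasting conditions or under fed conditions. Section 9.4.3.1 describes the comparison in the same way. The primary objective, however, names both conditions.

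**The concern.** The sample-size sections quote only 90%, while the SAP's success rule needs two independent groups to succeed together. Two independent events with probability about 0.9 each occur together with probability about 0.8. Someone who carried the 90% over to the overall conclusion would put the risk of failing at 10%. If the planning assumptions held exactly and drop-out were as planned, the risk would be 18% to 19%. At stake is how well the sponsor and readers understand the chance of reaching the conclusion in SAP 3.1.

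**Working it through.** **Inputs.** All come from protocol 9.2.2 and SAP 2.3 unless noted.
- True ratio T/R 0.95 in both parts; one-sided alpha 0.05.
- Limits 0.80 to 1.25 (protocol 9.1 and 9.4.3.1).
- Fasted: CV 19.1% for AUClast and 25.0% for Cmax; 38 evaluable, 48 recruited.
- Fed: CV 13.1% for AUClast and 18.7% for Cmax; 22 evaluable, 34 recruited.
- The AUClast/Cmax correlation is not given. It is assumed anywhere from 0 to near 1.

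**Method.** Exact power of two one-sided tests in a 2×2 crossover on the log scale: σ = √ln(1 + CV²), SE = σ√(2/N), df = N − 2, integrated over the chi-square distribution of the error variance.

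**Step 1: reproduce the plan's figures (Cmax).**
- Fasted: σ = √ln(1.0625) = 0.2462; SE = 0.2462 × √(2/38) = 0.0565; df = 36; power 0.909. At N = 36 it is 0.894, so 38 is the smallest even number reaching 90%.
- Fed: σ = √ln(1.03497) = 0.1854; SE = 0.1854 × √(2/22) = 0.0559; df = 20; power 0.906. At N = 20 it is 0.878, so 22 is the smallest even number.
- Recruitment: 38/0.80 = 47.5, giving 48; 22/0.65 = 33.8, giving 34.

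All stated figures are reproduced.

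**Step 2: add AUClast within each part.** AUClast power alone is 0.987 (fasted) and 0.995 (fed). Simulating both parameters together (400,000 replicates) for correlations from 0 to 0.99 gives a joint power of 0.898 to 0.909 in the fasted part and 0.902 to 0.907 in the fed part. The description of approximately 90% therefore also holds for the protocol's per-part hypothesis, which requires both parameters.

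**Step 3: combine the parts.** They are separate groups, so the probabilities multiply.

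| Evaluable (fasted, fed) | Cmax only | AUClast independent of Cmax |
|---|---|---|
| 38, 22 (planned drop-out) | 0.909 × 0.906 = 0.824 | 0.909 × 0.987 × 0.906 × 0.995 = 0.809 |
| 44, 28 (about half of planned) | 0.942 × 0.958 = 0.903 | 0.942 × 0.995 × 0.958 × 0.999 = 0.897 |
| 48, 34 (none) | 0.958 × 0.982 = 0.940 | 0.958 × 0.997 × 0.982 × 1.000 = 0.937 |

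Products use unrounded values. Half the planned drop-out gives 48 × 0.90 = 43.2 and 34 × 0.825 = 28.05; the table uses the even numbers 44 and 28. The two columns bracket the unknown correlation, which moves the result by about 1.5 points at 38 and 22 and by less at larger numbers.

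**Step 4: what a reported joint figure would change.** The estimates, 90% confidence intervals, analysis sets, alpha and pass/fail rule do not depend on the planned power. None of them would differ.

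**The case for a change.** The strongest case for acting is that this SAP, unlike a plan that leaves the two parts as separate claims, writes down an explicit joint rule and leaves its power unstated. The primary objective also covers both conditions, so the joint reading is natural. The like-for-like counterpart of 90% at 38 and 22 is 81% to 82%, and saying so would take one sentence.

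The arithmetic stands, and so does the observation that the figure is absent. The step from there to a defect does not. No stated number is wrong, and no sentence presents 90% as the power of the overall conclusion. That a reader would carry it over is a guess about readers: the documents show two separately labelled figures for two separate groups. The low end of the range also depends on the full planned drop-out in both parts, for which recruitment already makes allowance.

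The alternative route in SAP 3.2 is no answer to the concern. If its dissolution and sample-size conditions are assumed to be met, it lifts the Cmax product at 38 and 22 only from 0.823 to 0.826. Its minimum of 24 might exclude the fed part at 22 evaluable, depending on how that minimum is counted.

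The cost is also more than a sentence if protocol 9.2.2 is edited, because Appendix 2 requires ethics approval before an amendment is implemented.

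**Conclusion.** No change to the plan is needed. Power for the joint rule in SAP 3.1 is about 81% to 82% at the planned evaluable numbers, about 90% at half the planned drop-out and about 94% with none. This assumes a true ratio of 0.95 for both parameters in both parts, the stated CVs, independence between the parts, and an unknown AUClast/Cmax correlation that matters little. The figure is sensitive to the true ratio: the Cmax product at 38 and 22 would be 94.8% at a ratio of 1.00 and 61.0% at 0.92.

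The two 90% figures are correct for what they describe. The joint power is an unreported extra quantity that any statistician can derive from the documents. Reporting it would alter no enrolment target, analysis, error rate or conclusion. A team that wanted to could label the 90% as per part in SAP 2.3 and give the range above with its assumptions, but nothing in the trial depends on it.

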3.2 STATISTICAL DECISION RULES

When log transformation and statistical evaluation on comparative parameters of the reference and test drug except T_{max} are performed, the 90% confidence intervals for the difference in mean values between the test and reference should be within log 0.8 to log 1.25. Even if this is not the case, equivalence is achieved if all of the following conditions are met

- When the difference in average values of logarithmic AUC_{last} and C_{max} parameters to be assessed between two products are between log0.9 to log1.11.
- When the comparative dissolution test is conducted according to "Standard on Pharmaceutical Equivalence Study", all values are equivalent under all conditions described. However, products containing poorly soluble drugs and enteric-coated products containing poorly soluble drugs are not applicable to this provision. In case of extended-release products, the average dissolutions of the test drug are within that of the reference drug $\pm 10\%$ at three appropriate time points when the average dissolution of the reference drug are around 30%, 50%, and 80%.
- The total sample size of the bioequivalence study population is not less than 24 ($n=12/group$).

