9.1 Statistical Hypotheses

The following null hypothesis for the ratio of the geometric means will be used to assess bioequivalence

H0: $\mu T/\mu R \leq 0.8000$ or $1.2500 \leq \mu T/\mu R$ for at least one parameter (AUC_{last} or C_{max})

H1: $0.8000 < \mu T/\mu R < 1.2500$ for all parameters (AUC_{last} and C_{max})

where μT and μR are the geometric means for the test and reference treatment respectively.

The test treatment is Glucophage® XR Reduced Mass tablet and reference is Glucophage® XR tablet both under fasting condition (Part 1) or fed condition (Part 2).

- 1) The comparative evaluation parameters for the bioequivalence between the Test drug and the Reference drug are the area under the plasma concentration-time curve (AUC_{last}) and maximum plasma concentration (C_{max}). In this case, C_{max} is actually measured values and AUC_{last} is a calculated value by the trapezoidal rule.
- 2) When log transformation and statistical evaluation on comparative parameters of the Reference and Test drug except T_{max} are performed, the 90% confidence intervals for the difference in mean values between the Test and Reference should be within log 0.8 to log 1.25.
- 3) In the case of drop-outs, they are excluded from statistical analysis.
- 4) Separate hospitalization

For each study of Part 1 (Fasted state) and Part 2 (Fed state), if from the first administration of the first group to the first administration of second group is completed within 6 weeks, the effect of separate hospitalization is not considered. However, if it exceeds 6 weeks when separate hospitalization was arranged, the interaction by separate hospitalization has to be confirmed as follows.

The interaction by separate hospitalization has to use a model that sets period, sequence, treatment, group and group*treatment as a fixed effect and sets participant nested within sequence as a random effect.

At this time, if the group*treatment is not statistically significant (if it exceeds the significance level of 5%), the bioequivalence is evaluated by adding group as a fixed effect, and if the group*treatment is statistically significant, then the bioequivalence is evaluated by adding group and group*treatment as fixed effects. The cause of the interaction and the effect of the interaction on the evaluation of bioequivalence has to be closely checked.

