9.4.3 Other Analyses

9.4.3.1 Analysis of Primary Endpoints

Primary Variables: AUC_{last} and C_{max} of metformin

- An analysis of variance (ANOVA) model will be fitted for the log-transformed PK parameters C_{max} and AUC_{last} based on the PK analysis set. The model will include treatment, period, sequence, and participant within sequence as fixed effects. Treatment differences on the log scale will be estimated for C_{max} and AUC_{last} together with their 90% CIs. Point estimates and CIs will be back-transformed to the original scale for the comparisons.

The comparison will be the test treatment (Glucophage® XR Reduced Mass tablet) vs the reference treatment (Glucophage® XR tablet) under fasting conditions in Part 1, and under fed conditions in Part 2. The null hypothesis for non-bioequivalence will be rejected if the 90% CI for the ratio of the GeoMean lies within the interval 0.8000 to 1.2500 for all primary pharmacokinetic parameters.

The primary endpoints will be descriptively analyzed and graphical displays will be prepared. PK analyses will be specified in the Integrated Analysis Plan finalized before database lock.

In principle, analysis of variance shall be used at α (significance level) = 0.05.

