Section # and Name	Description of Change	Brief Rationale
4.1 Overall Design	Addition of a phrase related to separate hospitalization	Reflected the phrase for separate administration in case the recruitment of participants does not go smoothly.

CCI

6.4 Study Intervention Compliance	Addition of a phrase related to participants who are subject to statistics for separate hospitalization.	Reflected the criteria for the participants to whom additional statistics for separate hospitalization would be applied.
-----------------------------------	--	--

CCI

Protocol Version 5.0 (04-January-2021)

This amendment is nonsubstantial based on the criteria in Article 10(a) of Directive 2001/20/EC of the European Parliament and the Council of the European Union because it neither significantly impacts the safety or physical/mental integrity of participants nor the scientific value of the study.

Overall Rationale for the Amendment

Rationale Statement

Section # and Name	Description of Change	Brief Rationale
5 Study Population	Addition of a phrase of using external recruiting company by the request of the site.	For smooth recruitment of participants using external recruiting company by the request of the site.

Protocol Version 6.0 (08-July-2021)

This amendment is nonsubstantial based on the criteria in Article 10(a) of Directive 2001/20/EC of the European Parliament and the Council of the European Union because it neither significantly impacts the safety or physical/mental integrity of participants nor the scientific value of the study.

Overall Rationale for the Amendment

Rationale Statement

Section # and Name	Description of Change	Brief Rationale
4.2 Scientific Rationale for Study Design	Correction of Error, Update of Ordinance of the Prime Minister No. and MFDS Notification No.	Error Corrected. And reflected the latest Ordinance of the Prime Minister and MFDS Notification No.

9.1 Statistical Hypotheses	Deletion of phrases due to updated "Standard on Pharmaceutical Equivalence Study" Notification	Deleted the exceptions to follow the updated "Standard on Pharmaceutical Equivalence Study" Notification.
10 Comparative Dissolution Test Method	Deletion of a phrase due to updated "Standard on Pharmaceutical Equivalence Study" Notification	Deleted the exceptions to follow the updated "Standard on Pharmaceutical Equivalence Study" Notification.
11 References	Update of MFDS Notification No.	Reflected the latest MFDS Notification No

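### SAP 3.2 lets bioequivalence be declared after the 90% CI has failed; the current protocol has no such route

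*SAP*

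**What the plan says.** **Protocol.** Section 9.1, item 2, requires that "the 90% confidence intervals for the difference in mean values between the Test and Reference should be within log 0.8 to log 1.25". Section 9.4.3.1 says the same on the ratio scale: "The null hypothesis for non-bioequivalence will be rejected if the 90% CI for the ratio of the GeoMean lies within the interval 0.8000 to 1.2500". The rule there applies to every primary PK parameter. Neither section offers another route if the interval fails.

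**SAP 3.2.** It begins with the protocol's rule ("the 90% confidence intervals for the difference in mean values between the test and reference should be within log 0.8 to log 1.25") and continues: "Even if this is not the case, equivalence is achieved if all of the following conditions are met". There are three conditions, all of which must hold:

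- For AUClast and Cmax, the differences in log means of the "parameters to be assessed between two products are between log0.9 to log1.11".
- The comparative dissolution test shows equivalence. A separate criterion covers this type of product: "In case of extended-release products, the average dissolutions of the test drug are within that of the reference drug" plus or minus 10% at three time points.
- The total sample size is at least 24.

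**SAP 3.1.** "Overall, bioequivalence can be concluded if all 8 null hypotheses" are rejected at 5%. These are two one-sided hypotheses for each of two parameters in each of two parts.

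**Order of documents.** SAP section 2 says the plan follows the finally approved protocol. Its priority clause covers SAP against SOP only. The protocol's Appendix 8 records for version 6.0 (08-July-2021), against section 9.1: "Deleted the exceptions to follow the updated" Korean equivalence standard. SAP version 1.0 is dated 2021-11-30 and version 2.0 is dated 2022-04-08. The only change logged for version 2.0 is the blood sugar analysis.

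**The concern.** The trial has one primary objective, and the two governing documents contain different rules for deciding it. The difference matters only when the 90% CI has missed 0.80–1.25. The protocol then records failure, while the SAP can still record success. If that happened, someone would have to choose the rule with the result already known.

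The fallback also lacks what makes the CI rule valid. A 90% CI inside the limits is equivalent to two one-sided 5% tests, so the risk of passing a product whose true ratio lies on the limit is at most 5%. A window on the point estimate takes no account of its standard error. When precision is poor, an estimate can fall within 0.9–1.11 by chance although the true ratio is 0.80.

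**Working it through.** **Inputs.** From protocol 9.2.2: true ratio 0.95, one-sided alpha 0.05; Part 1 CV 25%, 38 evaluable, about 20% drop-out, 48 recruited; Part 2 CV 18.7%, 22 evaluable, about 35% drop-out, 34 recruited. From SAP 3.2: CI limits 0.80–1.25, point-estimate window 0.90–1.11, n at least 24. CVs above 25%, and 24 evaluable in either part, are assumptions used to show the range.

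**Model.** For a 2×2 crossover on the log scale, σw = √ln(1+CV²), SE = σw·√(2/n), df = n−2, and the 90% CI is the estimate ± t(0.95, df)·SE. Probabilities are exact: normal for the estimate, averaged over the chi-square distribution of the residual variance.

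**Step 1: the plan's own figures.** On the CI rule alone, CV 25% and ratio 0.95 give 90.9% power at n = 38, and 38/0.80 = 47.5, so 48. CV 18.7% gives 90.6% at n = 22, and 22/0.65 = 33.8, so 34. The stated sizes are reproduced without the fallback.

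**Step 2: can the two rules disagree?** Take n = 38, observed CV 40%, point estimate 0.90:

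- σw = √ln(1.16) = 0.385; SE = 0.385·√(2/38) = 0.0884; t(36) = 1.688.
- CI = 0.90·exp(±1.688·0.0884) = 0.775 to 1.045.

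This fails the protocol and meets the SAP's point-estimate condition. At n = 24 and CV 25%, the same estimate gives 0.797 to 1.017, again a split verdict.

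With the estimate at 0.90, the CI fails once t·SE exceeds ln(0.90/0.80) = 0.1178. That corresponds to an observed CV above about 24.1% (n = 24), 29.3% (n = 34), 31.1% (n = 38) or 35.4% (n = 48).

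**Step 3: how often?** P(SAP rule) = P(CI passes) + P(estimate in window) − P(both), for one parameter in one part with dissolution taken as matching.

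| n | CV | Ratio 0.80: CI rule | Ratio 0.80: SAP rule | Ratio 0.95: CI rule | Ratio 0.95: SAP rule |
|---|---|---|---|---|---|
| 48 | 25% | 5.0% | 5.0% | 95.8% | 95.8% |
| 38 | 25% | 5.0% | 5.0% | 90.9% | 90.9% |
| 38 | 30% | 5.0% | 5.4% | 79.5% | 81.2% |
| 38 | 35% | 5.0% | 6.9% | 66.2% | 74.0% |
| 38 | 40% | 5.0% | 9.2% | 52.3% | 69.2% |
| 34 | 18.7% | 5.0% | 5.0% | 98.2% | 98.2% |
| 24 | 25% | 5.0% | 5.9% | 73.9% | 78.7% |
| 24 | 30% | 5.0% | 8.5% | 55.8% | 71.0% |
| 24 | 35% | 4.7% | 11.5% | 37.8% | 65.4% |
| 24 | 40% | 3.9% | 14.3% | 22.5% | 60.6% |

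One line of the 24.1% case as an example, n = 24 and CV 30% at ratio 0.80: 4.97% + 8.22% − 4.75% ≈ 8.45%.

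**Step 4: Part 2 and the n condition.** Part 2 recruits 34 but plans on 22 evaluable. The SAP does not say whether its minimum of 24 counts randomised participants or the PK set. If it counts the PK set, a Part 2 that ends at its planned 22 cannot use the fallback while Part 1 can, and the two parts would be judged by different rules.

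**The case against.** The strongest reply is that the fallback would almost never act under the plan. At CV 25% and n = 38, power is 90.89% without it and 90.94% with it, and the error rate stays at 5.0%. CVs of 30–40% appear nowhere in the documents, and 24 evaluable in Part 1 means losing half of the 48 recruited. The error rates are also upper bounds for the overall claim, because the conditions must hold for both parameters, dissolution must match, and both parts must succeed. All of this stands, and it limits the expected numerical effect.

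Three textual points also stand in part. SAP 3.1 says equivalence can be concluded if all eight nulls are rejected, which read strictly is sufficient and not necessary; even so, 3.2 concludes equivalence with at least one null not rejected, which 3.1 does not provide for. The amendment log does not reproduce the deleted wording, so identifying it with the three SAP conditions is an inference, though the section, the subject and the dates all fit. And the Part 2 consequence depends on how the undefined study population is read.

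Finally, the SAP says it follows the approved protocol, so one could argue that the protocol's rule prevails. That is a reason to correct the text; it does not make 3.2 consistent. None of these points reconciles current SAP 3.2 with current protocol 9.1 and 9.4.3.1.

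**Conclusion.** The concern holds. The current SAP contains a route to the primary conclusion that the current protocol does not, and nothing in either document resolves the difference. The conflict rests on the current texts; the amendment log is supporting evidence only.

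The numerical effect is negligible at the planned CVs and numbers. It becomes material only if variability is higher or evaluable numbers lower than planned. That is also when the CI is most likely to fail and the fallback to be used. The inflation figures assume one limiting parameter in one part and matching dissolution. It must be fixed because the primary decision rule has to be single and settled before results are seen, whatever the probability of the divergent case.

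**What to change.** In SAP 3.2, delete the sentence that introduces the fallback and its three conditions. State that bioequivalence in each part is concluded only if the 90% CI of the test/reference geometric mean ratio lies within 0.8000–1.2500 for both AUClast and Cmax, as in protocol 9.1 and 9.4.3.1. In SAP 3.1, change the overall statement to only if, so that the two sections agree. Log the change as a SAP amendment made before results are available.

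The cost is SAP wording only. The design and sample size do not change, and the comparative dissolution test in protocol section 10 can proceed as planned. The sponsor gives up only a route that its current protocol does not offer.
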